Safety will be determined by the occurrence of any adverse events (AE) or serious adverse events (SAE). In accordance with the GCP decision tree for adverse event reporting all events will be reported to the sponsor and recorded to determine the safety of the intervention.

Utility will include eligibility (n = eligible/screened), recruitment (recruited/eligible), and adherence (number of patients completing the HIIT programme). The number of patients screened, recruited and commencing the HIIT programmes will be monitored at each hospital site. A register (if required, i.e. more than one patient attending), will be taken at each exercise class to record patient adherence and the completeness of each session will be recorded (i.e. how many minutes the patient completed). It is estimated that all patients should complete 18 sessions in total within 6 weeks. However, where any sessions are missed, the intervention period can be extended to 8 weeks to allow these sessions to be added on. Those not completing 18 sessions over the extended 8-week period will be deemed to have satisfactorily completed the intervention as long as they have completed >80% of the intervention (i.e. ≥ 15 out of 18 sessions). All patients completing the allotted 6-8 weeks for the intervention (regardless of whether they have completed \geq or < 15 sessions) will still be followed up. Those choosing to discontinue the intervention before completing the full intervention timeframe will be withdrawn.

Tolerability will be assessed by identifying if patients are able to reach and maintain the prescribed training range required to perform HIIT, for each full interval. Heart rate (HR) data will be collected throughout each HIIT session and saved on an encrypted USB stick this will then be compared to the 85-100%HRMax training range that has been prescribed – to determine if patients are able to achieve it. This range will be in line with an ongoing HIIT trial in CAD at 85-90% peak power output (PPO), aiming to achieve >85%HRMax, derived from CPET (15). If patients are not able to achieve 85-100%, this will determine the suitability of this HIIT protocol in this population. Reasons for stopping the HIIT exercise sessions (e.g. leg pain), will be recorded.

Secondary endpoints

Acceptability

Acceptability will be assessed by patient feedback using semi-structured interviews.

conducted using a sample of patients in three groups:

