Data obtained from all participants will be included in the data analysis and no data will be excluded on the basis of intervention and follow-up adherence. Therefore, all collected data at each time point will be analysed.

Baseline characteristics will be summarised descriptively using mean (\pm SD) for normally

distributed data and using median and range for non-normally distributed data. Categorical variables will be presented as frequency and percentages.

Rates of uptake, completion, dropout, adverse or serious adverse events and missing outcome data will be summarised and participation in the intervention will be described as the mean number of sessions attended and the mean time to completion (in weeks) to allow for comparison between actual and theoretical total intervention time.

In addition, tolerability will be assessed by comparing the mean heart rate achieved during each HIIT session to the 85-100% maximum heart rate range calculated from CPET.

Secondary endpoints such as changes in MWD, PFWD, VO_{2Peak} , VAT, ABPI and QoL at each time-point will be assessed using a repeated-measures general linear model.

All quantitative analyses will be conducted using the SPSS statistics software at the conventional two-sided 5% significance level with results presented as mean difference with 95% confidence intervals, associated *p* values and effect sizes where appropriate. Sub-group analysis will also be conducted comparing those who are able to give maximal effort during baseline CPET (and therefore able to perform maximal HIIT) and those who are not (therefore performing submaximal HIIT). Maximal effort will be based on previously published criteria (19, 38). Further sub-group analysis will also be performed comparing those who satisfactorily completed the intervention (i.e. completed $\geq 15/18$ sessions) and those who did not, presuming they do not withdraw from the intervention.

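### The planned comparison of patients with at least 15 of 18 sessions against those with fewer uses groups formed after baseline, so completers may look better even if extra sessions have no effect

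*Combined protocol and SAP*

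**What the plan says.** All references are to the combined protocol and SAP.

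- **The comparison.** Descriptive statistics and statistical analysis states: "Further sub-group analysis will also be performed comparing those who satisfactorily completed the intervention", defined as 15 or more of 18 sessions, "and those who did not, presuming they do not withdraw from the intervention".
- **The testing rule.** The same paragraph places all quantitative analyses "at the conventional two-sided 5% significance level", reported as mean differences with 95% confidence intervals, p values and effect sizes. The comparison is not labelled descriptive. No covariates are named for it and no limit is put on its interpretation.
- **When the groups are known.** Under the primary endpoint of safety, utility and tolerability, 18 sessions are expected in 6 weeks, but if any are missed "the intervention period can be extended to 8 weeks to allow these sessions to be added on". Completion status is therefore settled only at the end of treatment.
- **Who is left.** The same section states: "Those choosing to discontinue the intervention before completing the full intervention timeframe will be withdrawn". Patients who stay the full 6-8 weeks are followed up whether or not they reach 15 sessions.
- **The main analysis.** Data from all participants are analysed, with none excluded for poor adherence.

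**The concern.** Attendance is observed during treatment, so the two groups may differ in ways that also affect the outcome. The protocol gives leg pain as its example of why a HIIT session might be stopped. Walking distance, a secondary outcome, is limited by the same symptom. A patient who tolerates exercise well, is healthier or responds early may both attend more and improve more. Completers would then show larger gains even if the sessions separating the groups did nothing.

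The restriction "presuming they do not withdraw from the intervention" adds a second selection after baseline. The low-attendance group contains only patients who stayed for the full period with fewer than 15 sessions. Whether this widens or narrows the contrast cannot be determined from the documents.

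At stake is what the study may say about session number. A significant difference at a cut the protocol calls satisfactory completion could be taken as support for that cut when a later study is designed, and this comparison cannot provide such support.

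**Working it through.** **1. The plan's own threshold.** 15/18 = 83.3% and 14/18 = 77.8%, so 15 is the smallest whole number of sessions above 80%. The stated rule is consistent. The target of 50 + 20 = 70 patients also adds up. The protocol gives no power calculation or expected effect, so there is none to reproduce.

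**2. Timing.** Baseline tests come first, then 6-8 weeks of sessions, then the first follow-up visit. Completion status is fixed between the baseline and follow-up measurements. The other planned sub-group, maximal against submaximal effort at the baseline CPET, is defined at baseline and does not share the problem.

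**3. Size of the possible distortion.** The documents give neither the share completing nor any link between attendance and improvement. Both are assumptions here.

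- p = share completing at least 15 sessions
- r = correlation between a latent attendance propensity and improvement, both normally distributed
- true effect of sessions = 0
- q = standard normal quantile at 1 - p, and φ = standard normal density

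The expected difference in mean improvement, completers minus the rest, in SD units, is

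bias = r × φ(q) × [1/p + 1/(1 - p)] = r × φ(q) / [p(1 - p)].

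At p = 0.80: q = -0.842, φ(q) = 0.280 and p(1 - p) = 0.16, so bias = 1.75 × r.

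| Share completing | Multiplier | r = 0 | r = 0.2 | r = 0.3 | r = 0.4 |
|---|---|---|---|---|---|
| 60% | 1.61 | 0 | 0.32 | 0.48 | 0.64 |
| 70% | 1.66 | 0 | 0.33 | 0.50 | 0.66 |
| 80% | 1.75 | 0 | 0.35 | 0.52 | 0.70 |

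The result depends little on the assumed completion share and almost wholly on r. A negative r would reverse the sign.

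**4. Chance of a significant result with no session effect.** This was simulated as a two-sided 5% t-test on change with 80% completing, which is simpler than the repeated-measures model in the plan. Figures are good to a point or two.

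| Patients in the comparison | r = 0 | r = 0.2 | r = 0.3 | r = 0.4 |
|---|---|---|---|---|
| 70 (no withdrawals) | 5% | 21% | 42% | 67% |
| 56 (20% withdraw, assumed) | 5% | 18% | 34% | 55% |

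The error rate is nominal only when attendance is unrelated to improvement.

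**The case against.** The strongest reply is that the documents do not show the harm. Several parts of it stand.

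- **Response-driven attendance is an inference.** The leg-pain remark concerns stopping a session, not missing one. The section on potential risks and barriers names visit frequency, time, travel and parking, none of which is a response to treatment. The extension to 8 weeks lets missed sessions be made up, which could weaken any link with short-term symptoms. A reader might infer that completers are known to be the better responders; the documents do not establish that.
- **No threshold claim is made.** A reader might infer that the plan intends to show 15 sessions to be an effective dose. It does not say so. The cut is set in advance as a definition of satisfactory completion.
- **Group size is unknown.** It is tempting to call the low-attendance group small and unrepresentative. No expected number below 15 sessions, and no expected number of withdrawals, is given.
- **The magnitudes are conditional.** They follow from the chosen r, and at r = 0 there is no bias.
- **The reach is limited.** This is one sub-group analysis of secondary outcomes in a proof-of-concept cohort. The wording on reporting could also be read as making p values optional.

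What does not stand is the suggestion that nothing need change. Prespecifying the cut does not make the groups comparable. As written, the plan permits a 5% test with no stated purpose or limit, and nothing in the documents rules out a non-zero r.

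**Conclusion.** The point holds as a cheap improvement. The comparison can produce a completer advantage without any effect of sessions. With 80% completing, the spurious difference is 1.75 × r SD, from 0 at r = 0 to 0.70 SD at r = 0.4. Both the completion share and r are assumptions, so these figures show how sensitive the comparison is; they do not predict this trial's result. The selection caused by omitting withdrawers comes on top, with unknown direction.

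A reader might go further and conclude that the trial's main findings are compromised. The documents do not support that. Safety, utility and tolerability do not rest on this comparison, and the all-participant analysis excludes no data for adherence.

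**What to change.** In Descriptive statistics and statistical analysis, replace the tested comparison with a descriptive table by attendance group (15 or more sessions; fewer than 15 but stayed the full period), showing:

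- baseline characteristics;
- reasons for missed sessions, where known;
- baseline-adjusted change within each group with 95% confidence interval, without a between-group test.

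List patients who discontinued early separately, with baseline data and any recorded reasons only. Under Baseline and follow-up visits they are withdrawn and have no planned follow-up visits, so change cannot generally be shown for them.

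Add one sentence: the table does not estimate the effect of session number and does not support 15 sessions as an effective threshold. Baseline adjustment removes only differences captured by the baseline measures, so this sentence is needed even with the adjustment.

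The cost is a change of SAP wording and the loss of one between-group p value. No new visits or measurements are required.

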Peripheral arterial disease (PAD) is caused by occlusive atherosclerotic lesions of the arteries that supply blood to the legs (1, 2). The National Institute for Health and Care excellence (NICE) clinical guidance 147 notes that the incidence of PAD is approximately 20% in those over the age of sixty (3). The incidence is also high in certain populations such as diabetics, smokers and those with coronary artery disease (CAD) (3). However, some PAD patients may be asymptomatic, meaning that it's true incidence may be underestimated (2). There is an increased 10-year mortality risk associated with PAD, which is 3- and 6-fold for all-cause and CV mortality respectively, when compared to those with no evidence of the disease (4). One common symptomatic manifestation of PAD is a reproducible lower limb muscle pain on ambulation or during exercise known as intermittent claudication (IC). This is caused by reduced blood flow due to the narrowing of the arteries, resulting in an oxygen supply-demand imbalance (5, 6). The risk factors associated with IC are similar to those relating to myocardial infarction and angina pectoris such as smoking, hypercholesterolemia and diabetes (5). It is therefore unsurprising that within a cohort of 381 patients with lower extremity ischaemia, only 10% had normal coronary arteries identified via angiography (7).

What effect does it have on the patient?

IC can have a profoundly negative effect on a patient's life due to a number of factors, including a reduction in walking capacity, altered gait and balance and a likely reduction in muscle strength. In addition, this symptomatic disease affects functional capacity whilst also disrupting daily activities due to its restriction on ambulation (5, 8). A recent qualitative analysis explored patient experiences of IC and found that most patients described their symptoms as being detrimental to daily activities (9). Furthermore, research has demonstrated that IC can also have a negative effect on a patient's quality of life (QoL). In comparisons to members of the general population, IC sufferers have a worse QoL for all health aspects including; general health, vitality, social and physical functioning, physical role and bodily pain all of which are further reduced with increasing disease severity (10).

How is it diagnosed and managed?

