The HIIT intervention will be performed by using a cycle ergometer with exercise prescription based on the workload achieved during a cycle CPET. The use of a treadmill may preclude patients from reaching their prescribed HIIT training zones due to the onset of claudication whilst a cycle may reduce the risk of falls in very deconditioned patients (34). It has been demonstrated that the limiting symptoms during treadmill walking were often experienced in the leg, mainly the calf, whereas the limiting symptoms during cycling were much more varied (34). Furthermore, one study, albeit small, noted that cycle testing was better tolerated than treadmill testing, which is important considering that the HIIT training zone requires the patient to exercise to near-maximal levels, similar to during a CPET (35).

Inclusion criteria:

- Community dwelling adults aged 18 or over.
- ABPI <0.9 at rest or a drop of more than 20mmHg after exercise testing
- Ability to walk unaided
- English speaking and able to comply with exercise instructions

Exclusion criteria:

- Patients who are unable to provide informed consent
- Critical limb ischaemia/rest pain
- Active cancer treatment
- Significant comorbidities precluding participation in exercise testing and/or training as per the American College of Sports Medicine Guidelines (19).
- Resting/uncontrolled tachycardia (>100bpm) and/or Resting/uncontrolled hypertension (SBP >180mmHg or DBP >100mmHg)
- Symptomatic hypotension

Additional exclusion criteria

Further to analysis of CPET results, patients will be prevented from continuing their involvement in the study if there is indication of:

- Exercise-induced ischaemia or significant haemodynamic compromise.

N.B. – Patients who are able to perform a maximal effort CPET according to previously published guidelines (19) will undergo the intervention which will be prescribed on the basis of their initial CPET. This will be referred to as maximal HIIT.

Patients unable to perform a maximal effort CPET, will still undergo the intervention which will be prescribed on the basis of their initial CPET values, but will be referred to as submaximal HIIT.

Subject recruitment

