Patients who are deemed appropriate for referral to SEP as is usual practice will be informed of the research study evaluating HIIT as a novel exercise intervention for IC. Patients will then be sent a patient information sheet, detailing the aims and details of the study and what the intervention entails. Patients will then be contacted via telephone at least a week later to discuss their interest to undertake the intervention. Those who choose to participate in the study will be asked to attend for baseline assessment. Those who do not choose to partake in the research will be offered the usual SEP, without research. Those also declining the usual SEP will be referred back to their consultant.

Withdrawal of subjects

Participants are free to withdraw at any time and do not have to give a reason for doing so. If a participant exhibits any of the exclusion criteria or loses capacity to consent after enrolment on the study, they will be withdrawn. Full details of any withdrawal will be recorded in the case report form and withdrawal can occur at any time, including during the intervention or follow-up.

Trial exit

Patients will exit the trial if:

- They have completed their intervention and all follow-up assessments.
- They request or are unable to continue intervention or follow-up
- They suffer an adverse or serious adverse event meaning they are no longer able to continue
- They lose the capacity to consent
- They die.

General information**Potential patient benefits**

SEPs have proven to be effective for improving walking distance in patients with IC but are not always feasible or available (11, 14, 36). Other exercise interventions may provide a similar benefit and allow access for a greater number of patients. HIIT has demonstrated beneficial effects in the cardiac population (33, 37), which may be transferrable to the IC population, due to the similar disease aetiology. Therefore, patients may benefit from having a greater range of exercise options that may provide similar benefits, allowing them

to choose their preferred option, thus increasing availability and potentially uptake and adherence.

Potential risks/barriers to the patient

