The qualitative data will also be analysed using an inductive thematic analysis. Thematic analysis involves identifying, analysing and reporting themes that become apparent within the data (39). Themes collate important or patterned responses from within the data that are related to the research question (39). This means that as the researcher reads and re-reads the transcriptions, a pattern of responses will emerge that are related to the research question and can be grouped together under a theme heading. The approach will be inductive, which means that the themes are data-driven, thus emerging from the data, do not fit into a pre-existing coding frame and are not driven by the researcher's theoretical interest in the area (39).

In an attempt to minimise missing data from losses to follow-up patients will be contacted well in advance of their follow-up appointment and the researcher will attempt to rearrange any missed follow-ups. However, any missing data due to loss to follow-up will be recorded and reported adequately. Any missing data that should have been collected during a study visit will be investigated via source data and patient notes to exhaust all options. If data is still missing, it will be coded adequately during analysis and reported in results. Missing data will not be imputed by the researcher to avoid bias.

Safety reporting

Collecting and reporting data on adverse and serious adverse events will be in accordance with GCP and the Research Governance Framework v. 3.3, 2017.

Adverse events (AE)

An adverse event is any untoward occurrence that happens to a subject during the conduct of the study. The event may be as a result of the study conduct or intervention or there could be no relationship between the study and the AE at all.

Serious adverse events (SAE)

An AE is deemed serious if it:

- Results in death
- Is life-threatening (patient is at risk of death at the time of the event)
- Requires hospitalisation or prolongation of existing hospitalisation
- Results in persistent or significant disability or incapacity
- Consists of a congenital anomaly or birth defect

Hospitalisation that was planned before partaking in the study (i.e. elective surgery) should not be considered a SAE unless it has to be prolonged.

Reporting period:

The AE reporting period for each patient begins as soon as they have given informed consent for the trial and ends 30 days after their final study visit.

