The researcher will record any AE's upon knowledge of the event. Most events will occur outside of study activity and the site team will be informed at a later point. A discussion about the patient's general health will take place at each study visit to identify any AE's as patients may not inform the researcher about an event that they do not believe is related to the study, such as having a cold. Once knowledge of the event has been received, the researcher will gather as much information as possible and if necessary report to the sponsor.

Reporting serious adverse events

If a trial subject experiences a serious adverse event which in the opinion of the chief investigator is both

- **Related** - that is, it resulted from administration of any of the research treatments or procedures; and
- **Unexpected** - that is, the type of event is not listed in the protocol as an expected occurrence.

Then it will be reported to the Research Ethics Committee (REC) that gave a favourable opinion of the study and the Sponsor (Hull University Teaching Hospitals NHS Trust NHS Trust R&D department) **within 15 days** of the Chief Investigator becoming aware of the event using the non-CTIMP safety report form, available from:

<https://www.hra.nhs.uk/approvals-amendments/managing-your-approval/safety-reporting/>

Urgent safety measures

The chief investigator (or sponsor) may take appropriate safety measures to protect subjects from immediate hazard to their health or safety, without prior authorisation from a regulatory body. However, the chief/principal investigator must alert the sponsor (HEY R&D) as soon as possible of the urgent measures by contacting the R&D Office telephone number [name] or [name] (Mon - Fri 8am - 6pm) or the Trust Switchboard [name] (out-of-office hours) and asking for either the R&D Director or the R&D Manager.

The main REC will be notified immediately, at least within three days, by completing a substantial form and giving information about the measures taken and why.

Annual progress report:

An annual progress report will be submitted to the REC that gave the favourable opinion 12 months from the date of the favourable opinion. The relevant form, available from:

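### The SAE definition has no medically important criterion, so post-baseline ischaemia or significant haemodynamic compromise that leads to withdrawal can be classed as a non-serious AE

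*Combined protocol and SAP*

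**What the plan says.** Under Safety reporting, an AE is serious if it meets one of five criteria: "Results in death"; threat to life, explained as being at risk of death when the event happens; "Requires hospitalisation or prolongation of existing hospitalisation"; "Results in persistent or significant disability or incapacity"; or congenital anomaly. The list ends there. The same section says that collection and reporting follow GCP and a named governance framework, without restating how either defines seriousness.

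Under Additional exclusion criteria, a patient may not continue if CPET results indicate "Exercise-induced ischaemia or significant haemodynamic compromise". Withdrawal of subjects extends the exclusion criteria beyond entry: "If a participant exhibits any of the exclusion criteria or loses capacity to consent after enrolment on the study, they will be withdrawn".

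Under Reporting serious adverse events, the route to the Research Ethics Committee (REC) opens with "If a trial subject experiences a serious adverse event which in the opinion of the chief investigator is both" related and unexpected. Such an event is reported to the REC and the sponsor within 15 days. Unexpected means that the protocol does not list that type of event as expected.

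Safety is part of the primary endpoint and covers both AEs and SAEs. The statistical section summarises their rates, together with dropout.

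**The concern.** Safety is one of the questions this study exists to answer. The section on potential risks says that the safety of HIIT in claudication is unknown. The background cites a cohort of 381 patients with lower extremity ischaemia in which "only 10% had normal coronary arteries identified via angiography". The HIIT programme section expects that some patients will exceed their CPET peak heart rate in training, especially those who could not give a maximal CPET, and allows this with case-by-case monitoring. For those patients the baseline CPET may not have tested the heart rates that training reaches.

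Exercise-induced ischaemia and significant haemodynamic compromise are thus among the events that a reader of the safety results would most want to see. With the list as printed, such an event can end a patient's participation and still sit in the same class as a cold, which the protocol itself uses as an example of an AE. The report could state that no SAEs occurred although patients were withdrawn for ischaemia, and the REC would not receive the 15-day report.

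**Working it through.** The plan gives no figure to reproduce; the check compares the rules.

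**1. Can the event arise after baseline and lead to withdrawal?**
- At a CPET: yes, directly. The CPET/spirometry section schedules a cycle CPET with 12-lead ECG at every study visit, and the Additional exclusion criteria refer to CPET results.
- In a HIIT session: yes, but only through Withdrawal of subjects, which applies the exclusion criteria after enrolment. Heart-rate recording is the monitoring described during sessions, so recognition would rest mainly on symptoms. Reasons for stopping a session are recorded, and patients are observed for up to 10 minutes after the cool-down.

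**2. Is it an SAE?** Take an event that resolves on site:

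| Criterion | Met? |
|---|---|
| Death | No |
| Threat to life at the time | Only if the patient was then at risk of death |
| Admission or longer stay | No |
| Lasting or significant disability | Only if it leaves such a deficit |
| Congenital anomaly | Not applicable |

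If the two conditional answers are also no, the event meets none of the five and is an AE.

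**3. Who is told?**
- REC, 15-day report: the event must be serious, related and unexpected. The protocol contains no list of expected events, so one judged related to HIIT or to the CPET would pass the other two tests. Seriousness alone keeps it out.
- REC, urgent safety measures: notice within three days, but only if such measures are taken.
- Sponsor: the primary endpoint section says that every event is reported. The AE text under Safety reporting makes this depend on need. The two statements differ.
- Steering/data monitoring committee: meets every 6 months.

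**4. Scale.** The documents give no rate for these events. The recruitment target is 50 + 20 = 70. One event moved from AE to SAE would change the proportion of patients with an SAE by 1/70 = 1.4 percentage points, if that patient had no other SAE and all 70 are in the denominator. Consent precedes the baseline CPET, which can exclude patients, so fewer than 70 may start HIIT and the shift per event among starters would then be larger. This is the effect of one event, not a forecast of how many will occur.

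**The case against.** The case against a stronger reading is good, and most of it stands.

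- A reader might infer that such an event is an SAE only if the patient is admitted. That is wrong. Death, threat to life and lasting disability qualify without admission, and a severe ischaemic or haemodynamic event during exercise may well be life-threatening.
- A reader might infer that the protocol has a stopping rule for ischaemia in HIIT sessions. The rule concerns CPET results and reaches a session only through the general withdrawal sentence.
- A reader might infer that withdrawal implies seriousness, so that the plan contradicts itself. It does not. Other exclusion criteria, such as active cancer treatment or a resting heart rate above 100 bpm, would also lead to withdrawal without being SAEs in themselves, and Trial exit accepts that a non-serious AE can end participation.
- A reader might infer that the events vanish from the safety results or that the REC can never hear of them. They remain AEs in the primary outcome, withdrawal details go into the case report form, an independent committee reviews the data, and urgent safety measures have their own route to the REC.

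Two further points carry some weight. The cited GCP and governance texts may supply the missing criterion; the documents alone cannot settle this. But a general reference does not override a printed list, and site staff will work from that list. Also, coronary disease is likely to be common here, so classing every post-baseline ischaemic finding as an SAE could present background disease as harm in a cohort with no control group. That is a reason to leave the classification to the investigator, not a reason to omit the criterion.

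**Conclusion.** The gap is real but narrow. The SAE list has no medically important criterion, so post-baseline ischaemia or significant haemodynamic compromise that leads to withdrawal is only an AE unless one of the five listed criteria is met. The consequences are confined to how the primary safety outcome divides into AEs and SAEs, and to whether the 15-day REC report is triggered. The total number of recorded adverse events is unaffected.

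How many events would be reclassified cannot be stated from the documents. The conclusion rests on reading the printed list as complete, and on applying the exclusion criteria after enrolment as the withdrawal section says. The change is worth making because it costs almost nothing and concerns a primary outcome.

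**What to change.** 1. Add a sixth criterion to the SAE definition: any other event that the investigator judges medically important. Name exercise-induced ischaemia and significant haemodynamic compromise after baseline as examples to be assessed against it, not as automatic SAEs.
2. State that naming these examples does not make them expected for the purpose of the REC report. Otherwise the new text could itself close the 15-day route.
3. In the safety summary of the statistical section, show withdrawals for these two events on their own line, whatever their final classification.
4. Keep findings at the baseline CPET, before any HIIT, as screening exclusions. The AE period starts at consent, so say also that a baseline event meeting one of the five existing criteria remains an SAE.
5. Reconcile the primary endpoint section with the AE text under Safety reporting on whether all events, or only some, go to the sponsor.

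The cost is a few sentences and one table row, a few more SAE forms, and possibly a higher reported SAE rate. The number of patients, the visits and the analysis model do not change.
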